16.1 Secondary pharmacodynamic endpoint analyses

Serum and urine sampling for HS quantification will be performed at Baseline, Weeks 2, 3, 4, 8, 12, 16, 20, and 24 or at ET. CSF sampling for HS concentrations will be performed at Baseline, Weeks 12 and 24 or at ET.

16.2 Presentation of concentration data for HS in serum, urine, and CSF

16.2.1 Handling of missing data

Missing concentration data for all patients will be considered as non-informative missing and will not be imputed. No concentration estimates will be provided for missing sample values.

For concentration summary in all matrices, the following rules will apply:

- LLOQ values for HS concentrations in all matrices will be imputed as 0 for all time points where observed.

No further imputation will be applied to any missing values.

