8.4.3 Baseline and change from baseline

Baseline is defined as the last available assessment prior to 1st infusion of study treatment.

Change from baseline = (post-baseline value – baseline value).

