16.2.2 Listing and Presentation of individual PD data

HS concentrations in serum, urine, and CSF will be listed for SAF. The same listings will also contain change from baseline values for all time points. Baseline will be defined as HS concentration in each matrix before the administration of the 1st dose of SOBI003. Flags will be used to show deviations from protocol with the explanation in the footnote.

The actual sampling time of PD serum, urine or CSF sample collection will be listed for each treatment and will include the deviation in time from the protocol scheduled time, if applicable.

Individual subject serum, urine and CSF concentration data will be listed by subject, age, body weight, gender, time point and treatment (in relevant concentration units). The following figures will be produced for individual data for SOBI003:

- Individual serum and urine HS concentration-time profiles will be presented, for each treatment with all patients in the same figure on linear scale vs Week number. Profiles for patients within the same treatment will be combined.
- Scatter plots of HS concentrations in CSF for Weeks 12 and 24 for different treatments.

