16.2.3 Summary of HS concentrations in serum, urine, and CSF

HS serum, urine, and CSF concentration data will be summarized by treatment using the following descriptive statistics: n, number and % of LLOQ, arithmetic mean, SD, CV%, minimum, median and maximum, Q1 and Q3. In addition, results will be presented by demographic characteristics, e.g., age group and bodyweight, as applicable.

Samples taken outside the allowed time windows may be excluded from summarization. This will be determined prior to database lock.

Mean \pm SD HS concentrations in serum, urine and CSF vs Week number profiles will be presented, combining the curves for all dose levels within the same figure.

The HS levels including change from baseline will also be summarized by visit and time point using descriptive statistics. The HS change from baseline will also be presented as percentages.

The conventions presented in [Table 9](#) for PK parameters will also be used for the presentation of the descriptive statistics of HS serum concentrations.

17 Changes from protocol

- Schedule of events tables [Table 1](#), [Table 2](#), [Table 3](#), and [Table 7](#) have been updated according to protocol clarification letters
- According to the protocol linear mixed models were planned to be used to assess the PD effect of different dose levels of SOBI003 on HS levels in CSF, serum, and urine. Because of the discontinuation of the program modelling will be not be performed.

18 References

- 1 ICH Topic E9. Statistical principles for clinical trials (CPMP/ICH/363/96). March 1998: <http://www.ich.org/products/guidelines/efficacy/article/efficacy-guidelines.html>
- 2 Committee on Professional Ethics of the American Statistical Association. Ethical Guidelines for Statistical Practice dated 2016. Available from: <http://www.amstat.org/ASA/Your-Career/Ethical-Guidelines-for-Statistical-Practice.aspx>
- 3 Van de Kamp JJP, Niermeijer MF, von Figura K and Giesberts MAH. Genetic heterogeneity and clinical variability in the Sanfilippo syndrome (types A, B and C). *Clinical Genetics*. 1981; 20: 152-60.
- 4 Community-University Partnership for the Study of Children, Youth, and Families (2011). Review of the Vineland Adaptive Behavior Scales-Second Edition (Vineland-II). Edmonton, Alberta, Canada.
- 5 NCS Pearson (2006). Bayley Scales of Infant and Toddler Development-Third Edition. Green Valley Drive Bloomington, Minnesota, USA.

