14.3.4.8 Immunogenicity

Table 14.3.4.8.1	Number (%) of Patients with Anti-Drug Antibody (ADA) and Neutralizing Antibody (NAb) in Serum by Visit – Immunogenicity Analysis Set
Table 14.3.4.8.2	Number (%) of Patients with Anti-Drug Antibody (ADA) and Neutralizing Antibody (NAb) in Cerebrospinal Fluid (CSF) by Visit – Immunogenicity Analysis Set
Figure 14.3.4.8.3	Immunogenicity: Patient plots over Time – Immunogenicity Analysis Set

14.3.4.9 PK

Table 14.3.4.9.1	Summary of PK concentrations by Dose, Visit and Time point – PK Analysis Set
Table 14.3.4.9.2	SOBI003 PK parameters by Dose, Visit – PK Analysis Set
Table 14.3.4.9.3	Attainment of Steady State for SOBI003 using Repeated Measures ANOVA – PK Analysis Set

Table 14.3.4.9.4	Dose Proportionality for SOBI003 PK parameters by Visit using Humel Power Analysis – PK Analysis Set
Table 14.3.4.9.5	Dose Proportionality for SOBI003 PK parameters by Visit using Pearson Correlation Analysis – PK Analysis Set
Figure 14.3.4.9.6	Individual Serum PK Concentration-Time Profiles at Week 1, 4, 12, and 24 by Dose Level in Linear and Log-Linear Scales – PK Analysis Set
Figure 14.3.4.9.7	Mean (SD) Serum PK Concentration-Time Profiles at Week 1, 4, 12, and 24 by Dose Level in Linear and Log-Linear Scales – PK Analysis Set
Figure 14.3.4.9.8	Individual Trough and End of Infusion Serum PK Concentrations by Dose Level in Linear and Log-Linear Scale – PK Analysis Set
Figure 14.3.4.9.9	Mean (SD) Trough and End of Infusion Serum PK Concentrations by Dose Level in Linear and Log-Linear Scale – PK Analysis Set
Figure 14.3.4.9.10	Scatter Plots of Cerebrospinal Fluid PK Concentrations at Week 12 and 24 by Dose Level – PK Analysis Set
Figure 14.3.4.9.11	Regression/Scatter Dose Proportionality for SOBI003 in Log-Log and Linear-Linear Scales – PK Analysis Set
Figure 14.3.4.9.12	Regression/Scatter Dose Proportionality for SOBI003 in Linear-Linear Scales – PK Analysis Set

14.3.4.10 PD

Table 14.3.4.10.1	Heparan Sulphate (HS): Summary by Visit and Change from Baseline – Safety Analysis Set
Table 14.3.4.10.2	Summary of Heparan Sulphate (HS) Concentrations by Visit and Time point - Safety Analysis Set
Figure 14.3.4.10.3	Individual Serum Heparan Sulphate (HS) Concentration-Time Profiles by Dose Level in Linear and Log-Linear Scales – Safety Analysis Set
Figure 14.3.4.10.4	Individual Urine Heparan Sulphate (HS) Concentration-Time Profiles by Dose Level in Linear and Log-Linear Scales – Safety Analysis Set

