Figure 14.3.4.10.5	Mean (SD) Serum Heparan Sulphate (HS) Concentration-Time Profiles by Dose Level in Linear and Log-Linear Scales – Safety Analysis Set
Figure 14.3.4.10.6	Mean (SD) Urine Heparan Sulphate (HS) Concentration-Time Profiles by Dose Level in Linear and Log-Linear Scales – Safety Analysis Set
Figure 14.3.4.10.7	Mean (SD) Cerebrospinal Fluid (CSF) Heparan Sulphate (HS) Concentration-Time Profiles by Dose Level in Linear and Log-Linear Scales – Safety Analysis Set
Figure 14.3.4.10.8	Scatter Plots of Cerebrospinal Fluid Heparan Sulphate (HS) Concentrations at Week 12 and 24 by Dose Level – Safety Analysis Set

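### Setting HS results below LLOQ to zero turns any such post-baseline value into a reported 100% reduction

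*SAP*

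**What the plan says.** SAP 16.2.1 gives one rule for censored HS data in serum, urine and CSF: "LLOQ values for HS concentrations in all matrices will be imputed as 0 for all time points where observed". The SAP's abbreviation list explains LLOQ as a result below the assay's limit, so the meaning is clear. The rule is introduced as applying to the concentration summary.

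SAP 16.2.3 describes that summary. The statistics are "n, number and % of LLOQ, arithmetic mean, SD, CV%, minimum, median and maximum, Q1 and Q3". The same section summarises HS levels with change from baseline by visit, and adds: "The HS change from baseline will also be presented as percentages". SAP 8.4.3 defines change as the post-baseline value minus the baseline value. No separate rule covers censored values in change or percent change.

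SAP 17 drops the linear mixed models that the protocol planned for HS: "Because of the discontinuation of the program modelling will be not be performed".

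The figure list in SAP 19.2 (14.3.4.10 PD) includes "Individual Serum Heparan Sulphate (HS) Concentration-Time Profiles by Dose Level in Linear and Log-Linear Scales" and "Mean (SD) Cerebrospinal Fluid (CSF) Heparan Sulphate (HS) Concentration-Time Profiles by Dose Level in Linear and Log-Linear Scales". SAP 16.2.2, by contrast, describes the individual serum and urine profiles "with all patients in the same figure on linear scale vs Week number".

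**The concern.** The treatment is meant to lower HS. Of all the values a censored result could take, zero is the one that shows the largest reduction, so the error runs in one direction only, in favour of the drug.

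Change from baseline in HS is the endpoint of the third secondary objective (SAP 3.4.2). With the mixed models gone and the population PK/PD model reported outside the CSR (SAP 3.4.3), the HS analysis in the CSR consists of descriptive statistics, listings and plots. SAP 4.1 gives three patients in each of the two cohorts to be analysed, so one substituted value is a third of a cohort mean. No between-cohort HS difference is a specified output. But if censoring falls mainly on the higher-dose cohort, a reader comparing cohorts sees a larger dose contrast than the data support.

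Two cases have no rule at all. A baseline set to zero makes percent change a division by zero. A zero also cannot be placed on a logarithmic axis.

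**Working it through.** The plan states no figure on this point, so there is none to reproduce.

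**Inputs.**
- Censored HS set to 0: SAP 16.2.1.
- Change = post-baseline minus baseline: SAP 8.4.3.
- Percent change reported: SAP 16.2.3. No formula is given; the usual one is used here.
- Three patients per cohort: SAP 4.1.
- Assumed: L = LLOQ/baseline, with a quantifiable baseline B.

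**One patient.** Percent change = 100 × (x − B)/B. With x set to 0 this is 100 × (0 − B)/B = −100% for every B > 0. If the true x lies between 0 and LLOQ, the true reduction lies between 100(1 − L)% and 100%. Hence:

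- zero reports a 100% reduction: overstated by 0 to 100L points;
- LLOQ/2 reports 100(1 − L/2)%: error between −50L and +50L points;
- LLOQ reports 100(1 − L)%: understated by 0 to 100L points.

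The absolute change is overstated by the unknown x, that is, by up to one LLOQ in concentration units.

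**Mean of three, one affected.** Divide by 3.

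| Assumed L | Zero: max per patient | Zero: max in mean | LLOQ/2: max per patient | LLOQ/2: max in mean |
|---|---|---|---|---|
| 0.10 | 10 | 3.3 | ±5 | ±1.7 |
| 0.20 | 20 | 6.7 | ±10 | ±3.3 |
| 0.50 | 50 | 16.7 | ±25 | ±8.3 |

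**Example for the mean (assumed values).** L = 0.20; the affected patient is truly at −82%, the other two at −60% and −50%.
- True mean: (−82 − 60 − 50)/3 = −64.0
- Zero: (−100 − 60 − 50)/3 = −70.0
- LLOQ/2: (−90 − 60 − 50)/3 = −66.7
- LLOQ: (−80 − 60 − 50)/3 = −63.3

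The median is −60 in all four cases.

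**Median.** With one of three affected, the median moves only if that patient did not already have the largest reduction. Take L = 0.80, the affected patient truly at −30%, the others at −60% and −50%. The median is −50 in truth, −60 under zero, −60 under LLOQ/2 and −50 under LLOQ. With two of three affected, the zero rule makes the median −100%.

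**Contrast between cohorts (illustration).** Protocol 7.4.5 predicts brain HS reductions at 6 months of about 45% at 3 mg/kg and 80% at 10 mg/kg, and Protocol 7.5.7.3 expects CSF to mirror brain. Assume L = 0.25 and every patient at the prediction. Cohort 1 keeps 55% of baseline and is quantifiable. Cohort 2, at its planned dose, keeps 20% and is censored. The true contrast is 80 − 45 = 35 points. The zero rule shows 100 − 45 = 55, and LLOQ/2 shows 87.5 − 45 = 42.5.

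**The case against.** The strongest point is that nothing shows the rule will be triggered. Patients are described as having elevated CSF HS (Protocol 7.5.7.3). The predicted reductions leave about 55–65% of baseline at 3 mg/kg and 20–25% at 10 mg/kg, so on those averages no CSF value falls below LLOQ at L = 0.10 or 0.20. This stands as a limit on size. It does not cover individual patients who differ from the prediction, nor serum and urine, for which no prediction is given.

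Second, the rule is worded for the concentration summary, and the table index separates HS concentrations from HS change. The -100% is therefore an inference. But SAP 16.2.3 treats change and percent change within the HS concentration summary. If the rule did not reach them, the endpoint would have no rule for censored values. Either reading needs an added sentence.

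Third, the censoring is disclosed: the number and percentage below LLOQ are tabulated, individual values are listed, and there are only six patients and no HS test. A careful reader could spot the affected values. The means and percent changes still carry the zeros.

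Fourth, LLOQ/2 is itself a substitution. SAP 15.5.1 uses it only for pre-dose values on log-scale PK graphs, so it is not a precedent for summaries. In the L = 0.80 example it does not repair the median. That is why a second table with LLOQ substituted is needed beside it.

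Fifth, total HS in serum and CSF is built from selected disaccharides (Protocol 7.5.7.1.1), and LLOQ might apply to each one. The documents do not say so, and SAP 16.2.1 refers to HS concentrations.

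Finally, a cohort mean is zero, and so undrawable on a log axis, only if all its values are censored. That is correct. Individual values meet the problem singly, and the linear versus log-linear mismatch between SAP 16.2.2 and the figure list remains.

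**Conclusion.** The concern holds. On the natural reading of SAP 16.2.1 with 16.2.3, every post-baseline HS result below LLOQ with a quantifiable baseline is reported as a 100% reduction. The error is one-sided and at most 100 × LLOQ/baseline points per patient, or a third of that in a cohort mean with one of three affected. Its actual size is unknown: it depends on an LLOQ and baselines that the documents do not give, and it is nil if no result is censored. The missing rules for a censored baseline and for zeros on log-scale figures do not depend on that ratio, but matter only if such values occur. Any loss of contrast when both cohorts are censored comes from the censoring itself, not from this rule. The change is worth making because HS is now reported only descriptively in very small cohorts and the correction is cheap.

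**What to change.** In SAP 16.2.1, replace the zero rule with substitution of LLOQ/2, flagged, and state that it applies to HS summaries, change, percent change and log-scale figures. For urine, where the assay reports HS relative to creatinine (Protocol 7.5.7.1.2), substitute in the HS concentration before dividing by that sample's creatinine. Repeat the percent-change table with LLOQ substituted, so that the reader sees the smallest reduction compatible with the data. Do not calculate percent change when the baseline is below LLOQ; list those patients.

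The cost is one or two SAP sentences and one extra table, with no new sampling. The urine laboratory must supply the HS LLOQ and each sample's creatinine. The reported reduction may look less favourable. LLOQ/2 can still err in either direction, by up to half the worst case of the zero rule, and the LLOQ table understates the reduction by up to 100 × LLOQ/baseline points.

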16.2.2 Listing and Presentation of individual PD data

HS concentrations in serum, urine, and CSF will be listed for SAF. The same listings will also contain change from baseline values for all time points. Baseline will be defined as HS concentration in each matrix before the administration of the 1st dose of SOBI003. Flags will be used to show deviations from protocol with the explanation in the footnote.

The actual sampling time of PD serum, urine or CSF sample collection will be listed for each treatment and will include the deviation in time from the protocol scheduled time, if applicable.

Individual subject serum, urine and CSF concentration data will be listed by subject, age, body weight, gender, time point and treatment (in relevant concentration units). The following figures will be produced for individual data for SOBI003:

- Individual serum and urine HS concentration-time profiles will be presented, for each treatment with all patients in the same figure on linear scale vs Week number. Profiles for patients within the same treatment will be combined.
- Scatter plots of HS concentrations in CSF for Weeks 12 and 24 for different treatments.

16.2.3 Summary of HS concentrations in serum, urine, and CSF

HS serum, urine, and CSF concentration data will be summarized by treatment using the following descriptive statistics: n, number and % of LLOQ, arithmetic mean, SD, CV%, minimum, median and maximum, Q1 and Q3. In addition, results will be presented by demographic characteristics, e.g., age group and bodyweight, as applicable.

Samples taken outside the allowed time windows may be excluded from summarization. This will be determined prior to database lock.

Mean \pm SD HS concentrations in serum, urine and CSF vs Week number profiles will be presented, combining the curves for all dose levels within the same figure.

The HS levels including change from baseline will also be summarized by visit and time point using descriptive statistics. The HS change from baseline will also be presented as percentages.

The conventions presented in [Table 9](#) for PK parameters will also be used for the presentation of the descriptive statistics of HS serum concentrations.

17 Changes from protocol

- Schedule of events tables [Table 1](#), [Table 2](#), [Table 3](#), and [Table 7](#) have been updated according to protocol clarification letters
- According to the protocol linear mixed models were planned to be used to assess the PD effect of different dose levels of SOBI003 on HS levels in CSF, serum, and urine. Because of the discontinuation of the program modelling will be not be performed.

18 References

- 1 ICH Topic E9. Statistical principles for clinical trials (CPMP/ICH/363/96). March 1998: <http://www.ich.org/products/guidelines/efficacy/article/efficacy-guidelines.html>
- 2 Committee on Professional Ethics of the American Statistical Association. Ethical Guidelines for Statistical Practice dated 2016. Available from: <http://www.amstat.org/ASA/Your-Career/Ethical-Guidelines-for-Statistical-Practice.aspx>
- 3 Van de Kamp JJP, Niermeijer MF, von Figura K and Giesberts MAH. Genetic heterogeneity and clinical variability in the Sanfilippo syndrome (types A, B and C). *Clinical Genetics*. 1981; 20: 152-60.
- 4 Community-University Partnership for the Study of Children, Youth, and Families (2011). Review of the Vineland Adaptive Behavior Scales-Second Edition (Vineland-II). Edmonton, Alberta, Canada.
- 5 NCS Pearson (2006). Bayley Scales of Infant and Toddler Development-Third Edition. Green Valley Drive Bloomington, Minnesota, USA.

19.1 Listings Index

The numbering of the listings will be such that they can be easily integrated into the CSR following ICH E3, Section 16.2.

16.2 PATIENT DATA LISTINGS

16.2.1 Patient Disposition

Listing 16.2.1.1	Patient Disposition (Part 1) – Screened Patients
Listing 16.2.1.2	Patient Disposition (Part 2) – Screened Patients
Listing 16.2.1.3	Patient Disposition – Screen Failures

16.2.2 Protocol Deviations

Listing 16.2.2.1	Protocol Deviations – Safety Analysis Set
------------------	---

16.2.3 Patients Excluded from the Analysis Sets

Listing 16.2.3.1	Violated Inclusion Criteria – Safety Analysis Set
Listing 16.2.3.2	Fulfilled Exclusion Criteria – Safety Analysis Set
Listing 16.2.3.3	Exclusion from Analysis Sets – Safety Analysis Set

16.2.4 Demographic Data

Listing 16.2.4.1	Demographics – Safety Analysis Set
Listing 16.2.4.2	MPS III History of Siblings – Safety Analysis Set
Listing 16.2.4.3	Historical MPS IIIA Diagnostic Procedures – Safety Analysis Set
Listing 16.2.4.4	Central Laboratory Confirmation of MPS IIIA – Safety Analysis Set
Listing 16.2.4.5	Central Laboratory Confirmation of MPS IIIA SGSH – Safety Analysis Set
Listing 16.2.4.6	Medical History – Safety Analysis Set
Listing 16.2.4.7	Prior and Concomitant Medication – Safety Analysis Set
Listing 16.2.4.8	Antihistamine – Safety Analysis Set
Listing 16.2.4.9	Anesthesia/Sedation – Safety Analysis Set

16.2.5 Compliance

Listing 16.2.5.1	Study Drug (SOBI003) Administration – Safety Analysis Set
Listing 16.2.5.2	Study Drug (SOBI003) Administration: Vial Numbers – Safety Analysis Set

16.2.6 Individual Efficacy Response Data

Listing 16.2.6.1	Vineland adaptive behaviour scales, second edition (VABS)-II – Full Analysis Set
Listing 16.2.6.2	Bayley Scales of Infant and Toddler Development, third edition (BSID-III) – Full Analysis Set
Listing 16.2.6.3	Kaufman Assessment Battery for Children (KABC-II) – Full Analysis Set
Listing 16.2.6.4	Magnetic Resonance Imaging (MRI) – Full Analysis Set
Listing 16.2.6.5	Pediatric Quality of Life Inventory (PedsQL) – Full Analysis Set
Listing 16.2.6.6	Children's Sleep Habits Questionnaire (CSHQ) – Full Analysis Set
Listing 16.2.6.7	Actigraphy (sleep pattern) – Full Analysis Set

16.2.7 Adverse Events Listings

Listing 16.2.7	All Adverse Events – Safety Analysis Set
----------------	--

16.2.8.1 Listing of individual laboratory measurements by patient

Listing 16.2.8.1.1	Laboratory Reference Ranges – Safety Analysis Set
Listing 16.2.8.1.2	Clinical Chemistry – Safety Analysis Set
Listing 16.2.8.1.3	Hematology – Safety Analysis Set
Listing 16.2.8.1.4	Coagulation – Safety Analysis Set
Listing 16.2.8.1.5	Urinalysis – Safety Analysis Set
Listing 16.2.8.1.6	Other – Safety Analysis Set

16.2.8.2 Other Safety Data

Listing 16.2.8.2.1	Vital Signs – Safety Analysis Set
Listing 16.2.8.2.2	Anthropometry (Height, Weight, Body Mass Index and Head Circumference) – Safety Analysis Set
Listing 16.2.8.2.3	Physical Examination – Safety Analysis Set
Listing 16.2.8.2.4	Neurological Examination – Safety Analysis Set
Listing 16.2.8.2.5	12-Lead Electrocardiogram (ECG) – Safety Analysis Set
Listing 16.2.8.2.6	Echocardiography – Safety Analysis Set
Listing 16.2.8.2.7	Immunogenicity in Cerebrospinal Fluid (CSF) – Safety Analysis Set
Listing 16.2.8.2.8	Immunogenicity in Serum – Safety Analysis Set
Listing 16.2.8.2.9	PK Sampling and Concentration Data – PK Analysis Set
Listing 16.2.8.2.10	PK Parameters – PK Analysis Set
Listing 16.2.8.2.11	PD assessments Heparan Sulfate (HS) in Cerebrospinal Fluid (CSF) – Safety Analysis Set
Listing 16.2.8.2.12	PD assessments Heparan Sulfate (HS) in Serum – Safety Analysis Set
Listing 16.2.8.2.13	PD assessments Heparan Sulfate (HS) in Urine – Safety Analysis Set
Listing 16.2.8.2.14	PD assessments Heparan Sulfate (HS) Sampling and Concentration Data – Safety Analysis Set
Listing 16.2.8.2.15	Cross Reactive Immunological Material (CRIM) status at Baseline – Safety Analysis Set

19.2 Tables and Figures Index

The numbering of the tables will be such that they can be easily integrated into the CSR following ICH Section 14.

